8.5.9 Assignment to Treatment

Throughout the screening period until allocation of a treatment number or treatment kit, subjects will be assigned a screening number. The screening number will be a number combining the site number plus the number assigned to a subject according to her/his chronological order of screening at that site. The screening number will be used as the subject identifier throughout the study. An IWRS will randomize subjects and assign the appropriate treatment number or kit number.

8.5.10 Unblinding Procedures

In case of emergency, the Principal Investigator can ask for unblinding of a subject, i.e., informing the nature of the investigational product (active or placebo) to which the subject has been assigned. Such procedures should only be utilized in emergency situations when the identity of the treatment

group must be known by the Investigator in order to provide appropriate medical treatment. Before unblinding the subject, the unblinding request will be sent to the chair of the DSMB, [name]. She will notify the study investigator, [name], if the unblinding is necessary for treatment. The unblinding will be done by our pharmacovigilance agent, [name].

Reasons for unblinding must be clearly explained and justified in the eCRF, along with the date on which the subject was unblinded.

Unblinding of the study can also be done at the request of the regulatory agency or DSMB at any point in the study for safety or other concerns. In this case, unblinding will be done by our pharmacovigilance agent, [name].

8.6 Efficacy and Safety Variables

8.6.1. Efficacy Measurements

8.6.1.1 Primary Efficacy Endpoint:

The primary efficacy endpoint will be each patient's maximum esophageal eosinophil count on all specimens obtained on the biopsy at the end of treatment (Visit 10), after milk reintroduction at Visit 9.

8.6.1.2 Secondary Efficacy Endpoints:

The following secondary efficacy endpoints will be assessed:

- The symptom score at the end of each treatment period at 11 and 22 months.
- The change in symptom score at the end of each treatment period at 11 and 22 months compared to baseline.
- Mean Esophageal Eosinophil Count which is the average of all of the samples taken at the end of each treatment period at 11 and 22 months.
- Percentage of subjects with ≤ 1 eosinophils/HPF (excellent response) at the end of each treatment period at 11 and 22 months.
- Percentage of subjects with 2-14 eosinophils/HPF (good response) at the end of each treatment period at 11 and 22 months.
- Percentage of subjects with ≥ 15 eosinophils/HPF (poor response) at the end of each treatment period at 11 and 22 months.
- Change in mean and maximum esophageal eosinophil count from baseline to the end of each treatment period at 11 and 22 months.
- Esophageal Endoscopy Score at the end of each treatment period at 11 and 22 months.
- Change in Esophageal Endoscopy score from baseline to the end of each treatment period at 11 and 22 months.
- Change in the Eosinophilic Esophagitis Quality of Life Score from baseline to the end of each treatment period at 11 and 22 months.
- Combination Score of four measures (Eosinophils/HPF, EREFS, investigator assessment and parental assessment of symptoms)
- Time to development symptoms after milk reintroduction at month 9 and 20.

- Changes in exploratory biologic markers, including T-regulatory cells, TSLP, CBC with differential and milk-specific Immunoglobulin level, as well as epigenetics.

8.6.2 Safety Measurements

The following safety criteria will be determined:

- Adverse events (AEs) and Serious Adverse Events (SAEs) by system organ class, preferred term, severity and relatedness to Viaskin® Milk.
- Duration of local Viaskin® Milk-induced AEs, as assessed by the subjects.
- Use of medications to control local AEs.
- Systemic allergic symptoms and relatedness to Viaskin® Milk.
- Laboratory data, physical examinations and vital signs.

9. STUDY EVALUATIONS BY VISIT

Subjects with known established Eosinophilic Esophagitis (EoE) based on 2011 consensus diagnosis criteria will be considered for participation in the study. All subjects for whom a written informed consent has been obtained will enter the screening period, and only subjects who fulfill all eligibility criteria will be eligible and randomized for the double-blind treatment period. The duration of the screening period may vary among subjects and will be dependent of the exact duration of the milk-introduction period (from 1 week to 2 months) and of the duration of the milk- diet period (minimum of 6 weeks).

All screening records for potential eligibility by the gastroenterology collaborators will be reviewed and confirmed before entry into the double-blind treatment period; thereafter, dates of all study visits will be scheduled relative to the date of entry into the double-blind treatment period (Visit 4).

9.1 Visit 1: Screening

At the time of the screening Visit 1, the following assessments/procedures will be performed:

- Signed written informed consent for screening questionnaires, CBC, CMP and chart review. Medical history (including milk allergy history, other allergies, diet history).
- Demographics (including weight in kg and height in cm).
- Physical examination (including a complete skin examination).
- Vital signs (including heart rate, blood pressure, respiratory rate, and temperature).
- Eosinophilic Esophagitis Symptom Score (see Section 11.12).
- Blood collection for laboratory tests (hematology, biochemistry).
- Urine pregnancy test for female of childbearing potential.
- Milk introduction (30 ml/day for 1 week to 2 months) while the subject is on a proton pump inhibitor.
- Dietary History.
- Record all AEs (volunteered or in response to an open question) since the ICF was signed.

- Record prior (over last six months) and all concomitant medications.

9.2 Visit 2: Screening; 1 week to 2 months after Milk Re-Introduction

Subjects will have a minimum of two standard of care upper endoscopies and biopsy performed to confirm the diagnosis of Eosinophilic Esophagitis. They will have an upper endoscopy from 1 week to 2 months after introduction of a minimum of 30 ml of milk daily into their diet, and while on proton pump inhibitor. When the subjects are symptomatic, they will have an endoscopy 1-2 weeks after symptoms occur. We will review the medical records to review the number of eosinophils in the esophageal biopsy. Research parts of the visit will include EoE Quality of life measures and research blood samples. Subjects' clinical care GI and Allergy physicians will determine the order of screening standard of care endoscopies.

The following assessments/procedures will be performed:

- Physical examination (including a complete skin examination).
- Vital signs (including heart rate, blood pressure, respiratory rate, and temperature).
- Eosinophilic Esophagitis Symptom Score (see Section 11.12).
- Milk-free Diet.
- Diet History.
- Eosinophilic Esophagitis (Age-specific) Quality of Life Measure (Appendix 2).
- Upper endoscopy and biopsies of the esophagus, stomach and duodenum (see section 11.8) with upper endoscopy score (Appendix 2).
- Record all AEs (volunteered or in response to an open question).
- Record of all concomitant medications.

9.3 Visit 3: Screening; Minimum 6 weeks after Removing Milk

Subjects will have a minimum of two standard of care upper endoscopies and biopsy to confirm milk induced EoE performed, after a minimum of 6 weeks under milk-free diet and while on proton pump inhibitor. Results of the standard of care endoscopy and biopsy will be obtained by review of medical records. Research procedures at this visit include EoE Quality of life measure, and collection of any AEs. Subjects' clinical care GI and Allergy physicians will determine the order of screening standard of care endoscopies.

The following assessments/procedures will be performed:

- Physical examination (including a complete skin examination).
- Vital signs (including heart rate, blood pressure, respiratory rate, and temperature).
- Eosinophilic Esophagitis Symptom Score (see Section 11.12)
- Eosinophilic Esophagitis (Age-specific) Quality of Life Measure (Appendix 2).
- Milk-free Diet
- Diet History
- Upper endoscopy and biopsies of the esophagus (see Section 11.8) with upper endoscopy score (Appendix 2)
- Record all AEs (volunteered or in response to an open question).
- Record of all concomitant medications.

9.4 Visit 4: Eligibility/Randomization Treatment Period; Day 1

Visit 4 corresponds to the first day of treatment.

The following assessments/procedures will be performed:

- Review Pathology reports of the upper endoscopy and biopsy. Confirm eligibility by chart review of clinical records/randomize subject.
- Physical examination (including a complete skin examination).
- Vital signs (including heart rate, blood pressure, respiratory rate, and temperature).
- Eosinophilic Esophagitis Symptom Score (see Section 11.12).
- Urine pregnancy test for female of childbearing potential.
- Milk-free Diet
- Dispense diary cards (instruct subject how to complete).
- Dispense the first treatment box of investigational product to the subject.
- The investigator will take one Viaskin® patch from the box, apply the first Viaskin® to the subject, and train the subject on the proper technique and timing for applying the other patches.
- The subject will remain either in the CHOP clinic exam room or in the waiting room for at least 3 hours under observation. Patients will regularly be assessed by study staff. Should a patient experience an adverse reaction, or emergency, the patch will immediately be removed and the site cleaned. Patient will then be treated per CHOP allergy clinic emergency procedures.
- Check the skin under the Viaskin® and grade any local skin reaction after 1 hour after the patch is applied (see Section 11.13).
- Take a photograph of the site of application of the Viaskin® and keep it in the subject's medical records or source documents
- Record all AEs (volunteered or in response to an open question).
- Record all concomitant medication(s).

The subject may be discharged after a minimum observation period of 3 hours.

9.5 Visits 5, 6 and 7: Treatment Period; Day 8 (\pm 3 days), Month 1 (\pm 7 days), Month 3 (\pm 14 days)

The following assessments/procedures will be performed:

- Physical examination (including a complete skin examination).
- Vital signs (including heart rate, blood pressure, respiratory rate, and temperature).
- Eosinophilic Esophagitis Symptom Score (see Section 11.12).
- Milk-free Diet
- Record all AEs (volunteered or in response to an open question).
- Record all concomitant medication(s).
- Dispense diary cards (re-instruct subject on use if necessary).
- Review 'diary' and ensure that the diary has been completed accurately and that the subject is comfortable with using the diary.
- Check unused medication and assess medication compliance.
- Dispense the new treatment box to subject. Apply one Viaskin® patch to subject.
- Check skin under the Viaskin® and grade any local skin reaction (see Section 11.13).
- Take a photograph of site(s) of application of Viaskin® and keep in the subject's medical records or source documents.

The subject may be discharged after a minimum observation period of 1 hour (for Visit 5 only). There is no specific observation period required for Visits 6 or 7.

9.6 Visit 8: Treatment Period; Month 6 (\pm 14 days)

The following assessments/procedures will be performed:

- Physical examination (including a complete skin examination).
- Vital signs (including heart rate, blood pressure, respiratory rate, and temperature).
- Eosinophilic Esophagitis Symptom Score (see Section 11.12)
- Blood collection for laboratory tests (hematology, biochemistry)
- Milk-free Diet
- Record all AEs (volunteered or in response to an open question).
- Record all concomitant medication(s).
- Dispense diary cards (re-instruct subject on use if necessary).
- Review 'diary' and ensure that the diary has been completed accurately and that the subject is comfortable with using the diary.
- Check unused medication and assess medication compliance.
- Dispense the new treatment box to subject. Apply one Viaskin® patch to subject.
- Check skin under the Viaskin® and grade any local skin reaction (see Section 11.13).
- Take a photograph of site(s) of application of Viaskin® and keep in the subject's medical records or source documents.

9.7 Visit 9: Treatment Period; Month 9 (\pm 14 days)

The following assessments/procedures will be performed:

- Physical examination (including a complete skin examination).
- Vital signs (including heart rate, blood pressure, respiratory rate, and temperature).
- Eosinophilic Esophagitis Symptom Score (see Section 11.12)
- **Milk reintroduction (similar amount and duration as done during the screening period)** while the subject is on a proton pump inhibitor.
- Dietary History.
- Record all AEs (volunteered or in response to an open question).
- Record all concomitant medication(s).
- Dispense diary cards (re-instruct subject on use if necessary).
- Review 'diary' and ensure that the diary has been completed accurately and that the subject is comfortable with using the diary.
- Check unused medication and assess medication compliance.
- Dispense the new treatment box to subject. Apply one Viaskin® patch to subject.
- Check skin under the Viaskin® and grade any local skin reaction (see Section 11.13).
- Take a photograph of site(s) of application of Viaskin® and keep in the subject's medical records or source documents.

9.8 Visit 10: Treatment period; (1 week to 2 months after Visit 9, 3rd endoscopy)

Subjects will have an upper endoscopy and biopsy performed at this visit. They will have an upper endoscopy from 1 week to 2 months after reintroduction of a minimum of 30 ml of milk

daily into their diet, and while on proton pump inhibitor, as done during the screening period. When the subjects are symptomatic, they will have an endoscopy 1-2 weeks after symptoms occur.

The milk consumption should be equivalent to what the subjects were taking at the beginning of the study.

Visit 10 corresponds to the last day of double-blind treatment and the start of open-label treatment period. Standard Operating Procedures will be followed for endoscopy procedure⁶⁷. Patients will need to be healthy for this procedure. Any subject who has had a viral upper respiratory infection or gastroenteritis within 7 days will need to be rescheduled.

The following assessments/procedures will be performed:

- Physical examination (including a complete skin examination).
- Vital signs (including heart rate, blood pressure, respiratory rate, and temperature).
- Eosinophilic Esophagitis (Age-specific) Quality of Life Measure (Appendix 2)
- Eosinophilic Esophagitis Symptom Score (see Section 11.12)
- Blood collection for laboratory tests (hematology, biochemistry)
- Urine pregnancy test for female of childbearing potential.
- Diet History
- Upper endoscopy and biopsies of the esophagus (see Section 11.8) with upper endoscopy score (Appendix 1)
- Record all AEs (volunteered or in response to an open question).
- Record all concomitant medications.
- Dispense diary cards (re-instruct subject on use if necessary).
- Review 'diary' and ensure that the diary has been completed accurately and that the subject is comfortable with using the diary.
- Check unused medication and assess medication compliance.
- Check skin under the Viaskin® and grade any local skin reaction (see Section 11.13)
- Take a photograph of site(s) of application of Viaskin® and keep in the subject's medical records or source documents.
- Dispense the new treatment box to subject. Apply one Viaskin® patch to subject. It is permitted at the discretion of the Investigator, to postpone the application of the first patch up to a maximum of 7 days after V10.

9.9 Visit 11: Treatment period; 8 days (± 3 days) after visit 10

The following assessments/procedures will be performed:

- Physical examination (including a complete skin examination).
- Vital signs (including heart rate, blood pressure, respiratory rate, and temperature).
- Eosinophilic Esophagitis Symptom Score (see Section 11.12)
- **Milk diet options**
 - If the 3rd upper endoscopy (Visit 10) has ≥ 15 eosinophils/HPF isolated in the esophagus, the subject will stop milk consumption
 - If the 3rd upper endoscopy (visit 10) has < 15 eosinophils/HPF, the subject may continue milk consumption at the previous levels as per Investigator's recommendations.
- Dietary History.

- Record all AEs (volunteered or in response to an open question).
- Record all concomitant medication(s).
- Dispense diary cards (re-instruct subject on use if necessary).
- Review ‘diary’ and ensure that the diary has been completed accurately and that the subject is comfortable with using the diary.
- Check unused medication and assess medication compliance.
- Dispense the new treatment box to subject. Apply one Viaskin® patch to subject.
- Check skin under the Viaskin® and grade any local skin reaction (see Section 11.12).
- Take a photograph of site(s) of application of Viaskin® and keep in the subject’s medical records or source documents.

9.10 Visits 12, 13, and 14: Treatment Period; Month 1 (± 7 days), Month 3 (±14 days), Month 6 (±14 days),

The following assessments/procedures will be performed:

- Physical examination (including a complete skin examination).
- Vital signs (including heart rate, blood pressure, respiratory rate, and temperature).
- Eosinophilic Esophagitis Symptom Score (see Section 11.11).
- Milk-free Diet (if applicable)
- Record all AEs (volunteered or in response to an open question).
- Record all concomitant medication(s).
- Dispense diary cards (re-instruct subject on use if necessary).
- Review ‘diary’ and ensure that the diary has been completed accurately and that the subject is comfortable with using the diary.
- Check unused medication and assess medication compliance.
- Dispense the new treatment box to subject. Apply one Viaskin® patch to subject.
- Check skin under the Viaskin® and grade any local skin reaction (see Section 11.13).
- If the subjects develops symptoms of EoE, they may support milk during this period

9.11 Visit 15: Treatment Period; Month 9 (±14 days) after visit 10

The following assessments/procedures will be performed:

- Physical examination (including a complete skin examination).
- Vital signs (including heart rate, blood pressure, respiratory rate, and temperature).
- Eosinophilic Esophagitis Symptom Score (see Section 11.12)
- **Milk reintroduction (similar amount and duration as done during the screening period) if not already on milk**
 - **Otherwise, continue the current milk dose** while the subject is on a proton pump inhibitor.
- Dietary History.
- Record all AEs (volunteered or in response to an open question).
- Record all concomitant medication(s).
- Dispense diary cards (re-instruct subject on use if necessary).
- Review ‘diary’ and ensure that the diary has been completed accurately and that the subject is comfortable with using the diary.
- Check unused medication and assess medication compliance.

- Dispense the new treatment box to subject. Apply one Viaskin® patch to subject.
- Check skin under the Viaskin® and grade any local skin reaction (see Section 11.13).
- Take a photograph of site(s) of application of Viaskin® and keep in the subject's medical records or source documents.

9.12 Visit 16: Treatment period; 1 week to 2 months after Visit 15

Subjects will have an upper endoscopy and biopsy performed at this visit. They will have an upper endoscopy from 1 week to 2 months after reintroduction of a minimum of 30 ml of milk daily into their diet, and while on proton pump inhibitor, as done during the screening period. If subjects develop symptoms between visits 11 and 14, they will also restart milk with the same milk consumption should be equivalent to what the subjects were taking at the beginning of the study.

Visit 16 corresponds to the last day of treatment. Standard Operating Procedures will be followed for endoscopy procedure⁶⁷. Patients will need to be healthy for this procedure. Any subject who has had a viral upper respiratory infection or gastroenteritis within 7 days will need to be rescheduled.

The following assessments/procedures will be performed:

- Physical examination (including a complete skin examination).
- Vital signs (including heart rate, blood pressure, respiratory rate, and temperature).
- Eosinophilic Esophagitis (Age-specific) Quality of Life Measure (Appendix 2)
- Eosinophilic Esophagitis Symptom Score (see Section 11.12)
- Blood collection for laboratory tests (hematology, biochemistry)
- Urine pregnancy test for female of childbearing potential.
- Diet History
- Upper endoscopy and biopsies of the esophagus (see Section 11.8) with upper endoscopy score (Appendix 1)
- Record all AEs (volunteered or in response to an open question).
- Record all concomitant medications.
- Dispense diary cards (re-instruct subject on use if necessary).
- Review 'diary' and ensure that the diary has been completed accurately and that the subject is comfortable with using the diary.
- Check unused medication and assess medication compliance.
- Check skin under the Viaskin® and grade any local skin reaction (see Section 11.13)
- Take a photograph of site(s) of application of Viaskin® and keep in the subject's medical records or source documents.

9.12.1 Telephone Calls:

- Patients will be called monthly between visit 5 and visit 16 to monitor for reoccurrence of symptoms while wearing the Viaskin® milk patch.
- When the subject has reoccurrence of symptoms after milk re-introduction (or maximum exposure of 2 months to milk), the research endoscopy will be scheduled.

9.13 Visit 17: End of Study; Visit 16 plus 2 weeks or Early Termination (\pm 3 days)

Visit 17 will be performed 2 weeks after Visit 16 for completers. This visit and assessments procedures have also to be performed for subjects prematurely withdrawn. This will be the End of Study Visit.

The following assessments/procedures will be performed:

- Physical examination (including a complete skin examination).
- Vital signs (including heart rate, blood pressure, respiratory rate, and temperature).
- Eosinophilic Esophagitis Symptom Score (see Section 11.11).
- Record all AEs (volunteered or in response to an open question).
- Record all concomitant medication(s).
- Collect and review ‘diary’ and ensure that the diary has been completed accurately.
- Check skin where the Viaskin® patch was applied and grade any local skin reaction (see Section 11.13).
- Take a photograph of site(s) of application of Viaskin® and keep in the subject’s medical records or source documents.

Additional days up to 21 days may be added to visit period if due changes in patient’s school calendar, vacation, or illness.

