endoscopies are required for clinical care purposes. Milk will be reintroduced into the diet of the subject after 9 months of treatment at equivalent amounts and duration as performed during the screening period. A third research upper endoscopy and biopsy will be performed at the end of the milk-reintroduction period. After the 3rd upper endoscopy, all subjects will continue treatment with open-label Viaskin® Milk (500 µg of milk proteins). Subjects with ≥ 15 eosinophils/hpf on the 3rd upper endoscopy will restart milk-free diet for 9 additional months while on treatment with active therapy. Then, they will reintroduce milk into their diet at equivalent amounts and duration as performed during the screening period, at which time a 4th upper endoscopy will be done. For subject with < 15 eosinophils/hpf on the 3rd upper endoscopy, they will continue on milk for up to 11 additional months (if symptoms re-appear, milk-free diet should restart) while on treatment with active therapy, at which time a 4th upper endoscopy will be done. A final follow-up visit will be done 2 weeks after completion of treatment and after the last endoscopy.

In total, during this study, eligible subjects will be required to attend 17 study visits.

In addition to endoscopy and biopsy, subjects will undergo other efficacy parameter assessments at months 1, 3, 6, 9, 11, 14, 17, 20 and 22. Key assessments of safety will be performed at each study visit including vital signs, physical examinations and laboratory assessments. In between visits, subjects will report safety data on the diary cards

STUDY POPULATION AND MAIN CRITERIA FOR INCLUSION/EXCLUSION:
Pediatric subjects, aged 4 to 17 years, with milk induced Eosinophilic Esophagitis will be enrolled and randomized following confirmation of all eligibility criteria.

Inclusion Criteria:

1. Subjects between 4 and 17 years of age at the time of signing the informed consent
2. Well-documented symptoms suggestive of EoE after ingestion of milk and currently following a strict milk-free diet.

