*: Visit 2 (screening period) Visit 10, and Visit 16 have to be performed after 1 week to 2 months of milk introduction. The milk introduction period should be the same, as much as possible, as compared to that which occurred during the screening period for an individual subject.

*During screening, a minimum of two standard of care endoscopy procedures will be performed to obtain milk EoE diagnostic results needed for study qualification. Scopes may be repeated if clinically necessary and may affect screening visit timelines and total time on study. The results of additional SOC endoscopies will be allowed to assess eligibility, if the endoscopies are required for clinical care purposes. The order of the endoscopies will be determined by clinical care.

**: Visit 4 can be performed as soon as the results of the upper endoscopy and biopsy at Visit 3 are available and confirmed eligibility into the study.

***: Procedures at Visit 17 have to be performed 2 weeks after Visit 16 for completers. These procedures have also to be performed for subjects prematurely withdrawing. This will also be their End of Study Visit.

****: Patients may be contacted via telephone calls or email between visits to monitor symptoms, when symptoms reoccur-research endoscopy will be scheduled. Telephone calls will be made monthly between visit 5 and 16

#: Milk free diet starts after the visit

[figure not shown]
*Milk free diet may be extended if additional SOC scopes are needed. As mentioned above, the order of the endoscopies will be determined by clinical care.

% Milk free if upper endoscopy ≥ 15 eosinophils/hpf isolated in the esophagus; may continue milk if upper endoscopy is < 15 eosinophils/HPF in the esophagus

1. Including history of milk allergy and other allergies.
2. Including weight (kg) and height (cm).
3. Including a complete skin examination.
4. Heart rate, blood pressure, respiratory rate, temperature.
6. Laboratory tests. Hematology: hemoglobin, hematocrit, platelets, red blood cells, white blood cells. Biochemistry: aspartate aminotransferase, alanine aminotransferase, total bilirubin, total protein, blood urea nitrogen, creatinine.
7. Urine pregnancy test for female of childbearing potential only.

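### Two garbled milk instructions in the open-label visit sections (9.10, 9.12) conflict, read literally, with the stop-milk-on-symptoms rule, and the V9–V10 call schedule is stated both as weekly and as monthly

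*Protocol*

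**What the plan says.** **Milk in the open-label year.** Children with fewer than 15 eosinophils/HPF at the third endoscopy may stay on milk. For them the Protocol Synopsis and SAP 2.1 give the same instruction: "if symptoms re-appear, milk-free diet should restart".

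The visit-level text runs as follows:

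- Protocol 9.9 (Visit 11) decides milk from the Visit 10 biopsy. Below 15 eosinophils/HPF, "the subject may continue milk consumption at the previous levels", as the investigator recommends. The flow-chart footnote uses the same criterion: "may continue milk if upper endoscopy is < 15 eosinophils/HPF in the esophagus". Neither mentions symptoms.
- Protocol 9.10 (Visits 12 to 14): "If the subjects develops symptoms of EoE, they may support milk during this period".
- Protocol 9.11 (Visit 15): "Milk reintroduction (similar amount and duration as done during the screening period) if not already on milk".
- Protocol 9.12 (Visit 16): "If subjects develop symptoms between visits 11 and 14, they will also restart milk with the same milk consumption should be equivalent". The sentence then runs on to the amount taken at the start of the study.
- The Table 3 timing footnote: "Visit 2 (screening period) Visit 10, and Visit 16 have to be performed after 1 week to 2 months of milk introduction".

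**Symptom calls between Visits 9 and 10.** Protocol 8.1 and SAP 2.5 specify weekly calls during this milk reintroduction. Protocol 9.12.1 and the Table 3 telephone footnote specify monthly calls from Visit 5 to Visit 16, with no exception for this interval. Under 9.12.1, symptoms after reintroduction prompt the research endoscopy. Under 9.8 that endoscopy is due 1 to 2 weeks after symptoms occur.

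**The concern.** Sections 9.9 to 9.12 are what staff follow at each visit. Taken at face value, 9.12 tells a child who becomes symptomatic to go back on milk, and 9.10 gives no usable instruction. Every randomized child has biopsy-proven milk-induced EoE, and Protocol 8.2 and 10.3 limit re-exposure in order to minimize symptoms. A visit instruction that can be read the other way is a safety-wording problem. It also leaves unclear what milk exposure lies behind the Visit 16 results.

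The call schedule matters for a different reason. Symptoms reported between Visits 9 and 10 set the timing of the biopsy that supplies the primary endpoint, and they feed the secondary endpoint of time to symptoms after reintroduction at month 9. If calls are a month apart, staff may hear of symptoms only after the 1-to-2-week target has passed.

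**Working it through.** **1. Milk rule: the texts side by side.**

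| Place | If symptoms recur in the open-label year |
|---|---|
| Synopsis; SAP 2.1 | Restart the milk-free diet |
| 9.9; flow-chart milk footnote | Silent (biopsy count only) |
| 9.10 | Unintelligible; possibly an error for 'stop', and even then 'may' is weaker than the Synopsis 'should' |
| 9.11 | Reintroduce at Visit 15 if off milk |
| 9.12 | Restart milk |

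The SAP is based on protocol version 7.0 and the protocol reviewed is version 8.0. That does not explain the conflict, because the version 8.0 Synopsis carries the same rule as the SAP. The protocol disagrees with itself.

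One sequence reconciles the rows: stop milk on symptoms, reintroduce at Visit 15, biopsy at Visit 16 after 1 week to 2 months of exposure. Three things support it. To restart presupposes having stopped, 9.11 provides for children who are off milk, and the 9.12 sentence directly follows the one on pre-endoscopy reintroduction. But the sequence has to be assembled from several sections, and section 9 has no clear instruction to stop milk for symptoms.

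**2. Call rule: size of the difference.** The plan gives no figure to reproduce. Inputs from the documents are a reintroduction window of W days, 1 week to 2 months (7 to 60.88 days, with a month of 30.44 days), and an endoscopy target of at most 14 days after symptoms. Assumptions are that onset is uniform over the window, that symptoms are learned only at a call or at Visit 10, and that Visit 10 closes the window.

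Share first heard of more than 14 days after onset = Σ max(0, gap − 14) / W, summed over the gaps between successive contacts.

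The protocol does not say when the monthly calls fall relative to Visit 9, so two alignments are shown:

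- *First call a full month after Visit 9.*
- *Calls counted from Visit 5.* Visit 5 (Day 8) is 7 days after Day 1 and Visit 9 is 9 × 30.44 = 273.96 days after it. The tenth call, at 7 + 9 × 30.44 days, falls 7 days after Visit 9.

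| W (days) | First call one month after V9 | Calls counted from V5 |
|---|---|---|
| 14 | 0% | 0% |
| 21 | 7/21 = 33% | 0% (gaps 7, 14) |
| 28 | 14/28 = 50% | 7/28 = 25% |
| 30.44 | 16.44/30.44 = 54% | 9.44/30.44 = 31% |
| 45 | (16.44 + 0.56)/45 = 38% | 16.44/45 = 37% |
| 60.88 | 32.88/60.88 = 54% | (16.44 + 9.44)/60.88 = 43% |

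Averaged over W uniform on 7 to 60.88 days:

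- First call one month after Visit 9: 36%
- Calls counted from Visit 5: 24%
- Call phase random: 26%

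The ceiling is 16.44/30.44 = 54%. With weekly calls no gap exceeds 7 days, so the share is 0% throughout.

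**The case against.** **The milk text is a copy-editing fault, not a rival design.** This largely stands. The Synopsis, SAP 2.1 and 9.11 together give the intended sequence, and 9.10 is unintelligible rather than contrary. A reader might infer that the protocol means to keep symptomatic children on milk until Visit 15. By the schedule that would be 9 − 8/30.44 = 8.7 months from Visit 11, or 8, 6 or 3 months from Visits 12, 13 or 14. The documents do not support that. It requires ignoring the Synopsis and every safeguard below, so those durations describe a misreading and do not estimate risk.

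**Safeguards exist.** This also stands:

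- A symptom score is taken at every open-label visit, and calls run to Visit 16.
- Symptoms after reintroduction prompt an endoscopy (9.12.1).
- Continuing milk is at the investigator's recommendation (9.9), and a Table 3 footnote ties continuation at Visits 10 and 16 to improvement.
- Worsening EoE symptoms bring a return visit (8.5.6).
- The investigator can withdraw a subject in the subject's best interest (8.4.3.1).
- Marked EoE symptoms in more than one patient suspend enrollment (8.4.3.2).

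There is also one site, experienced in EoE, so divergent readings across sites do not arise. Still, none of these safeguards tells staff to stop milk.

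**Milk intake is already captured.** Protocol 11.10 has subjects record milk daily once it is reintroduced, and the diary is reviewed at Visits 12 to 14. A stop date should be recoverable, so a dedicated field is optional.

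**The specific weekly rule overrides the general monthly one.** This is a reasonable reading, and weekly calling satisfies both statements. But no text gives it precedence, and neither monthly statement makes an exception.

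**No harm to the primary endpoint is shown.** Correct. A biopsy more than 14 days after symptoms can still fall within the permitted 1 week to 2 months on milk.

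**Conclusion.** The point holds as a minor clarification. Protocol 9.10 and 9.12 contain drafting errors in operative instructions which, read literally, conflict with the Synopsis and SAP 2.1. The probable intent is clear enough to correct the text without changing the design. What is at stake is open-label safety and the interpretation of the month-22 secondary endpoints. The documents give no relapse rate, so no number of affected children can be stated.

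The call schedule is a separate inconsistency, two places against two. Under the stated assumptions, monthly calls would leave an average of 24% (counted from Visit 5), 26% (random phase) or 36% (first call a month after Visit 9) of symptom onsets unheard for more than 14 days, against 0% with weekly calls. Neither 36% nor the 54% ceiling should be quoted alone, because both depend on an alignment of calls that the protocol does not specify. All these figures overstate delay if families report symptoms unprompted.

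A reader might also infer that the primary analysis or its power is compromised. The documents do not support this. The milk wording applies only after Visit 10, and the call rule can shift the timing of the Visit 10 endoscopy, but no resulting bias is shown.

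**What to change.** - **Protocol 9.10:** *If EoE symptoms recur, stop milk and restart the milk-free diet.*
- **Protocol 9.12:** *Subjects who stopped milk for symptoms between V11 and V14 re-introduce it at V15 at the screening amount and duration before the V16 endoscopy.*
- **Flow-chart milk footnote:** add the same symptom rule beside the eosinophil criterion.
- **Protocol 9.12.1 and the Table 3 telephone footnote:** *weekly during the V9–V10 milk reintroduction, monthly otherwise.*
- **Optional:** a milk stop-date field at Visits 12 to 14.

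The cost is a short clarifying protocol amendment with no new visits or procedures. SAP 2.1 and 2.5 already agree with the corrected text and need no change.
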